### **6.1 Adverse Event Definitions**

For the purposes of this study, reportable AEs include ocular AEs and non-ocular serious adverse events (SAEs). All AEs will be classified first for seriousness and significance and then as to whether or not they are device related or non-device related and if device related, then, if it is an adverse device effect (ADE), an anticipated serious adverse device effect (ASADEs) or an unanticipated serious adverse device effect (USADEs). AEs, ADEs, ASADEs, USADEs, SAEs, Significant Non-Serious AEs and Non-Significant Non-Serious AEs are defined as follows:

#### **6.1.1 Adverse Event (AE)**

Any untoward medical occurrence, unintended disease or injury, or untoward clinical signs (including abnormal laboratory findings) in subjects or users, whether or not related to the investigational medical device. Adverse events should be categorized as device related or non-device related.

Throughout the course of this study all efforts will be made to remain alert to reportable AEs. If an AE occurs, the first concern will be the safety of the subject and appropriate medical intervention will be made.

All reportable AEs occurring after signing of informed consent and through the subject's end of participation in the study must be reported. All reportable AEs must be followed until the event resolves or stabilizes.

#### **6.1.2 Serious Adverse Event (SAE)**

An adverse event which:

- Led to death;
- Led to serious deterioration in the health of the subject, that resulted in:
  - A life-threatening illness or injury; or
  - A permanent impairment of a body structure or a body function (e.g., blindness); or
  - Inpatient or prolonged hospitalization; or
  - Medical or surgical intervention to prevent life-threatening illness or
  - Injury or permanent impairment to a body structure or a body function; or
  - Chronic disease
- Led to fetal distress, fetal death, or a congenital abnormality or birth defect.

### 6.1.3 Serious Adverse Ocular Event

Serious Adverse Ocular Event is a serious adverse event that results in, or has potential to cause, either permanent impairment of an ocular function or damage to an ocular structure and may necessitate medical or surgical intervention. Serious Adverse Events require expedited reporting. Serious adverse events include any hazardous, **sight-threatening conditions** occurring after exposure to a study lens, including but not limited to the following:

- A presumed infectious ulcer (defined as a progressive erosion of the corneal tissue). For the purposes of reporting, a corneal ulcer which has *any* of the following characteristics should be considered in this category:
  - Central or paracentral location;
  - Penetration of Bowman's membrane;
  - Infiltrate  $\geq 2$  mm diameter;
  - Associated with iritis;
  - Associated with any increase in intraocular pressure;
  - Culture positive for microorganisms;
  - Increasing size or severity at subsequent visits.

*Note: Signs of a presumed infectious ulcer may include irregular focal infiltrates; active lesions with raised edges; significant diffuse infiltration; anterior corneal to mid-stromal involvement; erosion with overlying staining; conjunctival and lid edema; anterior chamber reaction (iritis); severe bulbar and limbal redness. Symptoms associated with a presumed infectious ulcer (microbial keratitis) may include pain of rapid onset; severe redness; purulent or mucopurulent discharge; tearing; photophobia.*

- Any central or paracentral (within 6 mm of cornea) corneal event that results in permanent opacification (such as corneal scar or vascularization)
- Any serious adverse ophthalmic events including hypopyon and hyphema.
- Any neovascularization within the central 6 mm of the cornea.
- Permanent loss of 2 or more lines (10 letters) of Best Spectacle Corrected Visual Acuity (BSCVA).
- All cases of iritis.

### 6.1.4 Significant, Non-Serious Adverse Event

A Significant, Non-Serious Adverse Event is an Adverse Event that does not meet the serious criteria, is considered significant, and requires expedited reporting. These events include (but are not limited to):

- Peripheral non-progressive non-infectious corneal ulcer
- All symptomatic corneal infiltrative events
- All cases of corneal staining severity greater than or equal to Grade 3
- A temporary loss of 2 or more lines (10 or more letters) of BSCVA (for greater than or equal to 2 weeks)

- Increase in neovascularization of 1.5mm or greater.
- Any ocular event that necessitates temporary lens discontinuation of greater than or equal to 2 weeks.

#### **6.1.5 Non-significant, Non-serious Adverse Event**

A Non-Significant Non-Serious Adverse Event may include (but are not limited to) and does not require expedited reporting:

- Asymptomatic, peripheral, corneal infiltrative events.
- Bacterial Conjunctivitis
- Viral Conjunctivitis
- Allergic Conjunctivitis
- Corneal Edema
- Contact Lens Related Papillary Conjunctivitis

#### **6.1.6 Adverse Device Effect (ADE)**

An ADE is an Adverse Event that is assessed to be related to the use of an investigational medical device. This definition includes Adverse Events resulting from insufficient or inadequate instructions for use; deployment, implantation, installation, or operation; or any malfunction of the investigational medical device. This definition also includes any event resulting from use error or from intentional misuse of the investigational medical device.

##### **6.1.6.1 Anticipated Serious Adverse Device Effect (ASADE)**

An ASADE is an ADE that first meets the serious criteria (see definition above for Serious Adverse Event) or significant, non-serious criteria (see above definition for significant, non-serious AE) and which, by its nature, incidence, severity or outcome, has been previously identified in the investigational plan or application (including a supplementary plan or application) and/or in the risk analysis report. ASADEs include:

- Corneal Ulcer (infectious or non-infectious)
- Keratitis
- Sensitivity to light (photophobia)
- Excessive eye secretions including mucopurulent discharge
- Blurred vision, rainbows or halos around objects
- Poor visual acuity (reduced sharpness of vision)
- Moderate to severe eye pain not relieved by removing the lens

##### **6.1.6.2 Unanticipated Serious Adverse Device Effect (USADE)**

An USADE is an ADE that first meets the serious criteria (see definition above for Serious Adverse Event) or significant, non-serious criteria (see above definition for significant, non-serious AE) and has an effect on health or safety or any life-threatening problem or death caused by, or associated with, a device if that effect, problem or death was not previously identified in nature, severity or degree of incidence in the investigational plan or application (including a supplementary plan or application), or any other unanticipated serious problem associated with a device that relates to the rights, safety, or welfare of subjects.

### **6.1.7 Device Deficiency**

Inadequacy of an investigational medical device with respect to its identity, quality, durability, reliability, safety, or performance. This includes malfunctions, use errors, inadequate labelling, insufficient or inadequate instructions for use. A Device Deficiency can occur with or without the occurrence of an Adverse Event.

### **6.2 Adverse Event Treatment and Culturing**

With any Adverse Event, treat the subject as appropriate to prevent further complications and to potentially resolve the event consistent with the standard of care.

A culture should be obtained in cases of corneal ulcer or suspected ocular infection, unless medically contraindicated. Cultures should be taken from the cul-de-sac, lower eyelid margin, and the corneal lesion (if applicable). When a culture is obtained, the contact lenses and contact lens cases which were being utilized by the subject at the time of the AE should be collected from the subject (if available at the time of the culture) for culturing and processing by the clinical laboratory designated by the Research Clinic. Microbial data generated from returned subject supplies (e.g., lenses, lens cases and/or lens case solutions) are for information only. Because microbes may be introduced into subject supplies during use, recovery of microbes from returned subject supplies cannot be presumed to indicate etiology or direction of organism transmission. The ocular cultures, along with the associated contact lenses and contact lens cases, will be sent to the clinical laboratory designated by the Research Clinic for analysis. The clinical laboratory will report the culture results to both the Investigator and to the Research Clinic, the Investigator will record the results in the applicable form.

### **6.3 Adverse Event Identification and Evaluation**

Throughout the course of a study all efforts will be made to remain alert to Adverse Events (AEs). If an AE occurs, the first concern will be the safety of the subject and appropriate medical intervention will be made. The associated product should be retained for further analysis, if needed.

All AEs occurring after signing the informed consent and through the end of the subject's participation in the study must be recorded and reported, if applicable. All AEs must be followed until the event resolves or stabilizes.

Identify potential adverse events during a clinical study by using the following sources:

- Direct observation by the Investigator
- Asking the study participant using a non-specific question (i.e. Have you had any problems since the last visit?)
- Unsolicited volunteering of information by the study participant (i.e. Doctor, I have had numerous headaches since I started using this lens)
- Laboratory or test results that meet protocol requirements for classification as an adverse event (i.e. IOP over 30mmHg)

- When evaluating AEs, the Investigator should classify the AE based on the following three criteria: **Seriousness and/or significance** (based on the criteria provided in Section 6.1)
1. **Severity:**
    - **Mild:** Subject awareness of a sign or symptom that is easily tolerated, requires no treatment, and does not interfere with subject's daily activities.
    - **Moderate:** Subject awareness of a sign or symptom which may be a low level of concern to the subject and may interfere with daily activities but can be relieved by simple therapeutic care.
    - **Severe:** A sign or symptom that interrupts the subject's daily activity and requires systemic therapy or other treatment.
  2. **Relationship of the event to the study device** using the following guidelines:
    - **Related:** There is at least a reasonable possibility that the AE is related to the study device (contact lens) and/or solution or rewetting drops. Reasonable possibility means that there is evidence to suggest a causal relationship or association between the study device and/or solution or rewetting drops and the AE. Also referred to as an ADE.
    - **Not Related:** There is little or no reasonable possibility that the AE is related to the study device (contact lens) and/or solution or rewetting drops. This assessment implies that the AE has no evidence to suggest either a causal relationship or association to the study device and/or solution or rewetting drops and a more likely or certain alternative etiology exists.
  3. **Expectedness of the event**
    - **Unexpected Adverse Event (UAE):** Unexpected Adverse Events must be reported to the IRB within 10 calendar days of discovery.
    - **Expected Adverse Event:** An adverse event of which, the nature or severity of which is consistent with the current product labeling, investigator brochure, data sheet, etc.

[Redacted]

[Redacted]

**6.5 Reporting Device Deficiencies**

[REDACTED]

[REDACTED]

## 7.0 STATISTICAL METHODS

### 7.1 Study Endpoints

The primary endpoint is Primary gaze orientation 5 minutes after lens insertion.

### 7.2 Hypotheses

[REDACTED]

### 7.3 Sample Size

[REDACTED]

#### **7.4 Randomization**

To minimize or avoid bias, subjects will be assigned randomization numbers as they are enrolled according to unique randomization schedules created for the study. The randomization schedule will be produced prior to study enrollment. Subjects will be receiving each of the study lens types once, in a randomized order.

The randomization schedule is verified up to 5 times during the course of the study: The CRT visually verifies the study material against the randomization schedule during CTM preparation (if applicable) and before dispensing any study materials. The randomization schedule is also verified in EDC after dispensing the CTM. Once the study is complete, randomization is verified again during CTM reconciliation. Upon completion of the study, the EDC programmer also verifies randomization.

#### **7.5 Study Populations**

Subjects will be included in all summaries under the treatment that they actually received. Analyses of safety data will include all dispensed subjects. All other summaries will include all eligible, completed subjects.

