Study Design	
Approximately 30 soft toric contact lens adapted subjects will be enrolled in this feasibility, bilateral, randomized, double-masked (subject and investigator), repeated measures insertion study. All subjects will be seen for a Screening/Dispensing Visit at which informed consent will be obtained and eligibility will be assessed. If subjects satisfy all eligibility criteria, subjects will be dispensed study lenses according to unique randomization tables that will be provided to each Investigator. If study eligibility is met, [REDACTED]
 
[REDACTED]
 
Subjects will be receiving each of the study lens types once, in a randomized order. [REDACTED]
 
[REDACTED]

Study Duration/ Follow-up	
There are a total of 4 study lens types. [REDACTED]
 
Visit 1: Approximately 45 minutes
 
The clinical investigation will take approximately 1 month to complete. Enrollment will take place throughout the duration of the study.

Treatment and Allocation Schedule	
There are a total of 4 study lens types. [REDACTED]

Subjects Planned	
Approximately 30 experienced soft contact lens wearing subjects (includes males and females). Healthy volunteers will be recruited and screened as per criteria outlined below. The subjects will all be experienced soft contact lens wearers.

Anticipated Study Population	
Recruitment for this study will target experienced contact lens wearers that have refractive error requiring contact lens correction. Healthy male and female volunteers will be recruited and screened as per criteria outlined below.

Inclusion Criteria	
To be eligible for entry into the study, the subject must:
 
 
1. Be 18 years or older on the date the Informed Consent Form (ICF) is signed and have capacity to read, understand and provide written voluntary informed consent.
 
2. Have physiologically normal anterior segments not exhibiting clinically significant biomicroscopy findings.
 
3. Have no active ocular disease or allergic conjunctivitis.
 
4. Not be using any topical ocular medications.
 
5. Be willing and able to follow instructions.
 
6. Have signed a statement of informed consent
 

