### **3.2.3 Subject Completion**

The subject will have completed the study when he/she has worn all of the study lens types. Subjects who require further follow-up due to an ongoing Adverse Event will be followed according to the Adverse Event Section 6.0.

The Investigator may discontinue a subject during the study for any reason if, in his or her opinion, it is in the best interest of the subject. Reasons for discontinuation include but are not limited to:

- adverse effects
- other ocular complications
- subject non-compliance
- subject request
- subject found to be ineligible during study participation\*

\*Any subject enrolled in the study, who later is found to have not met any of the eligibility criteria at entry, will be discontinued at the Sponsor's request.

Subject discontinuations will be documented clearly on the applicable case report form. Subjects that are discontinued from the study following randomization will not be replaced.

Exit visits should be completed for early terminated subjects.

The completion of the clinical investigation shall be deemed to coincide with the last visit of the last subject and when follow-up is complete.

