## **5.2 Study Completion**

The subject has completed the study when the subject has completed all of the study lens types. Subjects who require further follow-up will be followed according to the Adverse Event or Post- Study Follow-Up Section. There is no planned follow-up period after the clinical investigation is complete.

The completion of the clinical investigation shall be deemed to coincide with the last visit of the last subject and when follow-up is complete.

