## **6.0 ADVERSE EVENTS (AE)**

Subjects who experience an adverse event during study participation will be discontinued from study participation but will be followed by the Investigator until resolution of the adverse event or until the Investigator determines that further improvement is not expected.

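### Minor: Section 7.5 leaves out 5-minute orientation readings already recorded on subjects who exit before wearing all four lens types; keeping them is a nearly cost-free improvement.

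*Combined protocol and SAP*

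**What the plan says.** Section 7.1 sets the endpoint: "The primary endpoint is Primary gaze orientation 5 minutes after lens insertion". It is read separately on each lens. The Synopsis states "There are a total of 4 study lens types", each worn once in random order for about 10 minutes.

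Section 7.5 assigns safety data to all dispensed subjects and then says: "All other summaries will include all eligible, completed subjects". The primary endpoint falls under that sentence.

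Completion is defined per subject, in two places:
- Section 3.2.3: "The subject will have completed the study when he/she has worn all of the study lens types".
- Section 5.2: "The subject has completed the study when the subject has completed all of the study lens types".

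Early exit is foreseen. Section 3.2.3 lets the investigator discontinue a subject for adverse effects, other ocular complications, non-compliance, the subject's own request or ineligibility. Section 6.0 says: "Subjects who experience an adverse event during study participation will be discontinued from study participation". On replacement, Section 3.2.3 says: "Subjects that are discontinued from the study following randomization will not be replaced". Section 7.6.3 plans no exploratory or sensitivity analysis.

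Section 3.1 sets a target of 30 subjects completing each lens type. The hypotheses (7.2) and sample size (7.3) are redacted.

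**The concern.** In a four-lens repeated-measures design each lens contributes its own reading, so a subject can hold valid primary data on some lenses without finishing all of them. Section 7.5 turns one unfinished lens into the loss of every reading that the subject has given. No other visible population or analysis brings those readings back.

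What is at stake is precision in a sample of about 30. The question here is only what happens to readings taken before exit. Whether and when a subject should be discontinued is not questioned.

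**Working it through.** **No stated figure to reproduce.** Sections 7.2 and 7.3 are redacted, so no power, effect size, standard deviation or exit rate can be checked. The effect of the rule follows from the text; its size needs assumptions.

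**Step 1: who loses data.** Let m be the number of lenses with a recorded 5-minute reading at exit. A subject who stops during lens 1, 2 or 3 has m between 0 and 3, has not worn all four types, and is outside the 7.5 population. All m readings drop out. An exit during lens 4 is unclear: the subject may already have worn all types (3.2.3) without having completed them all (5.2). The figures below cover exits on lenses 1 to 3 only.

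**Step 2: how many readings.** The plan yields 30 × 4 = 120 subject-lens readings. One exit discards up to 3 recorded readings; three exits discard up to 9.

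**Step 3: how useful they are.** For a given pair of lenses, the chance that both were read before exit is C(m,2)/C(4,2): 0 for m = 1, 1/6 for m = 2, and 3/6 = 1/2 for m = 3.

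**Step 4: simple check of the completer rule.** With k exits from 30, the standard error (SE) of a paired contrast rises by √(30/(30−k)) − 1:
- k = 1: √(30/29) − 1 = 1.7%
- k = 2: √(30/28) − 1 = 3.5%
- k = 3: √(30/27) − 1 = 5.4%

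**Step 5: model-based comparison.** Assumptions, none of them from the documents:
- 30 subjects start;
- four lens orders, as nearly balanced as possible (30 does not divide by 4, so 7 or 8 subjects per order);
- generalised least squares on subject-lens means with lens and period effects;
- equal correlation between lenses of 0.3;
- SE averaged over the six lens pairs and over random choices of which subjects exit.

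Rise in SE against no exits:

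| Analysis | 1 exit | 2 exits | 3 exits |
|---|---|---|---|
| Completers only | 1.8% | 3.6% | 5.6% |
| All observed, m = 0 | 1.8% | 3.6% | 5.6% |
| All observed, m = 1 | 1.5% | 3.0% | 4.6% |
| All observed, m = 2 | 1.0% | 2.1% | 3.2% |
| All observed, m = 3 | 0.5% | 1.1% | 1.6% |
| All observed, spread | 1.2% | 2.5% | 3.7% |

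The spread case puts exits equally on lenses 1, 2 and 3, half before and half after minute 5. That gives m = 0, 1, 2, 3 with weights 1/6, 2/6, 2/6, 1/6. A hand check at three exits: (5.6 + 2 × 4.6 + 2 × 3.2 + 1.6)/6 = 3.8%, in line with the table.

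**Step 6: sensitivity and scale.** For correlation 0 to 0.6, the spread case at three exits runs from about 3.5% to 4.0%, and the completer figure stays at about 5.6%. In complete-subject terms, three exits leave 30/1.056² = 26.9 under the completer rule and 30/1.037² = 27.9 in the spread case, a gain of about one subject. With one exit the gain is about 0.6 percentage points of SE (1.8% against 1.2%).

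**The case against.** The strongest reply is that this hardly matters. The study is a feasibility study without pass/fail criteria, using experienced wearers for about 10 minutes per lens. A gain of about 2 points of SE needs three exits in 30, and nothing in the documents supports a 10% exit rate. This stands, and it is why the point is minor.

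Second, Section 3.1 expresses 30 as a number of completers, and the redacted 7.3 may allow for exits. If 30 do complete, the stated target is met. This also stands, although non-replacement means that it is not assured, and readings from those who exit would still be unused.

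Third, a completer set puts every lens mean on the same subjects, which is a defensible choice for descriptive summaries. That is a reason to keep the completer summary alongside. It is no reason to give the recorded readings no role at all.

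Fourth, bringing back every reading would also bring back those of subjects removed under Section 4.3.2 because non-compliance threatened the study's validity. That is right, and the fix needs an exception for it.

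A reader might also infer that exits will be common, because 6.0 discontinues subjects with an adverse event and 6.1.1 defines the term as "Any untoward medical occurrence, unintended disease or injury, or untoward clinical signs". The documents do not support that. Section 6.1 limits reportable events to ocular events and non-ocular serious events, and 3.2.3 says that the investigator may, not must, discontinue for adverse effects.

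**Conclusion.** The point holds as a minor, cheap improvement. On its visible and unredacted text, 7.5 read with 3.2.3 and 5.2 excludes 5-minute readings recorded before an early exit, and nothing visible restores them.

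For 1 to 3 exits among 30 starters, the SE of a lens contrast rises by about 2% to 6% under the completer rule. It rises by about 1% to 4% with all observed readings if exits are spread over lenses 1 to 3. These figures rest on an assumed exit count, a near-balanced order, a lens-and-period model and a between-lens correlation of 0 to 0.6. The reading of the rule is firm; the sizes are illustrative. With no exits, or exits only before the first reading, the two approaches agree.

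A reader might infer that the completer rule biases the comparison between lenses. The documents do not show this: no passage links the chance of exit to lens orientation, so selection bias is only a possibility. Nor can loss of power be claimed while 7.2 and 7.3 are redacted.

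**What to change.** In Section 7.5:

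1. Define the orientation analysis population as all randomized, eligible subjects with at least one recorded 5-minute reading. Exclude readings judged invalid for a documented reason, decided without knowledge of the lens worn, for example non-compliance that jeopardises validity under 4.3.2.
2. Analyse by the lens actually worn, using all observed readings in a within-subject model with lens and period. The exact form depends on the redacted 7.2.
3. Keep the completers-only summary as supportive.
4. Report exits by lens and period, and state whether each came before or after the 5-minute reading.

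The cost is a change of wording, with no extra data collection. The downside is that lens means no longer rest on an identical set of subjects and that the model needs a missing-at-random assumption. The completer summary shows whether either matters. If nobody exits, the change in population alters no result.
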